PEEP is defined as an elevation of transpulmonary pressures at the end of expiration. PEEP contributes to the re-opening of collapsed alveoli and opposes alveolar collapse thus improving V/Q matching (ventilation/perfusion ratio).

Indication studied

The investigators will test the hypothesis that RM during cesarean section, in women under general anesthesia improves lung compliance and gas exchange. The investigators will apply RM and leave PEEP at 8cmH₂O and ventilation with low tidal volume in pregnant women who decided to have a cesarean section under general anesthesia. The investigators believe and will try to prove that RM improves lung compliance.

Brief Description

This will be an Interventional, Prevention, Parallel Assignment, Double Blind (patient, caregiver, outcomes Assessor), Randomized; Safety/Efficacy Study. We will use two parallel groups of pregnant women. In the first group we will use RM, PEEP and low tidal volume during mechanical ventilation (RM Group) while in the second group (Control Group) we will use the standard method (not RM, not PEEP and “standard” tidal volume). The estimated duration of the study will be 6 months.

Patient Enrollment, Start and Completion date

Enrollment: 90 patients

Study Start Date: April 2015

Primary Completion Date: September 2015

Study Completion Date: September 2015

Protocol Identification

ClinicalTrials.gov Identifier: NCT01826968

Study ID Number: Lung Recruitment in Cesareans GHPyrgosRECProt [RECProt010113]

Principal Investigator and more information

[name], [name], PhD, General Hospital of Pyrgos, [contact], mob: [name]

Sponsor

General Hospital Of Pyrgos, [name], [contact]

Ethics

The Institutional Review Board will review and approve the study. The study will be performed in compliance with good clinical practice (GCP):

INTERNATIONAL CONFERENCE ON HARMONISATION OF TECHNICAL REQUIREMENTS FOR
REGISTRATION OF PHARMACEUTICALS FOR HUMAN USE

ICH HARMONISED TRIPARTITE GUIDELINE

STRUCTURE AND CONTENT OF CLINICAL STUDY REPORTS

Patient Information and Consent

Written informed consent will be obtained obtained from all patients at allocation.

Abbreviations

RM: Recruitment Maneuver

FRC: functional residual capacity

Com_{dyn}: Dynamic compliance

dv/dp: difference in alveolar volume/difference in inspiratory pressure

P_{peak}: Peak airway inspiratory pressure

PEEP: Positive end expiratory pressure

V/Q: ventilation/perfusion ratio

VILI: ventilation induced lung injury

GA: General anesthesia

ALI: Acute lung injury

SBP: Systolic blood pressure

DBP: Diastolic blood pressure

MAP: Mean arterial pressure

BPM: Beats per minute (heart rate)

ETCO₂: End tidal CO₂

ITT: Intension to Treat

LOCF: last observation carried forward

PCV: Pressure Control Ventilation

VCV: Volume Control Ventilation

Abstract

Introduction: In pregnant women the supine position, during cesarean section, reduces functional residual capacity (FRC) and worsens lung compliance. In a prospective randomized double-blind clinical trial the investigators will test the hypothesis that alveolar recruitment maneuver (RM) during cesarean section, and after delivery, in women under general anesthesia improves lung compliance. The primary end point of the study will be the improvement in dynamic lung compliance (dv/dp) while the improvement in gas exchange (increase in PO_2 , PO_2/FiO_2 , PH and SpO_2 and decrease in PCO_2 and end-tidal CO_2) and difference in P_{peak} will be the secondary endpoints of the study.

Materials and Methods: Women undergoing cesarean section will prospectively assigned to one of two groups. In the RM group, one minute after delivery, the investigators will apply RM: The ventilator will be switched to pressure control mode (from volume control) and the inspiratory time will be increased to 50%. The Positive End Expiratory Pressure (PEEP) will be increased up to 15cmH₂O and the Positive End Inspiratory Pressure (Ppeak) progressively will be increased up to 45cmH₂O. The whole RM will last 2 minutes. Then, volume control ventilation will be used again and PEEP step wise will be decreased to 8cmH₂O. Women in the RM group will be ventilated with low tidal volume after the RM (6 ml/kg). In the control group, the investigators will not use lung RM at all. Women in this group will be ventilated with higher tidal volume (8 ml/kg), which is a common tidal volume in everyday clinical practice. In both groups, lung compliance will be measured (dynamic compliance) as dv/dp (ml/cmH₂O). Measures will be assessed before RM but after delivery, 3 minutes after delivery and after recruitment, 10 and 20 minutes after recruitment. At all time points Ppeak, blood pressure, heart beats per minutes, oxygen saturation, end-tidal CO_2 and blood gas will also be measured too. In order to detect clinically meaningful differences, a power analysis will be conducted between the two study groups with regards to dynamic lung compliance (dv/dp), which is the primary outcome of the study. Women will be assigned to one of the two groups using computer-generated blocks.

Results and Discussion: Data will be presented as mean value (+/- SD) while $p < 0.05$ will be considered significant. Mixed Analysis of Variance will be used for comparisons between and within group. There will be no significant difference in lung compliance between groups before RM ($p > 0.05$). Two-sample t-test to compare the two groups at each time point will be used as supplementary analysis, while chi-square test for categorical variables and two-sample t-test for continuous variables for patient and procedural characteristics differences between the two groups, will be used. In the RM group, according to similar studies, the investigators are expecting to see a significant increase in lung compliance after RM compared to control group were RM was not applied. In the RM group the investigators estimate that dynamic lung compliance will be significantly higher at all time points (3 minutes, 10 and 20 minutes) compared to baseline compliance or compliance before RM too. In the control group there should be no significant difference in dynamic lung compliance at the different time points. There should be no significant demographic differences between groups while the investigators estimate that there will be no statistical or/and clinical significant differences in SpO_2 , blood gas, end-tidal CO_2 , Ppeak, and women hemodynamic.

Introduction

General anesthesia (GA) can cause changes in respiratory mechanics and lung function, which persist for days after surgery. These changes occur immediately after induction of anesthesia but are aggravated with mechanical ventilation¹⁻⁵. The reduction in lung compliance and the formation of atelectasis after the induction of GA is a significant cause of abnormalities in regional ventilation and gas exchange⁴. Two different types of atelectasis, compression atelectasis and resorption atelectasis, have an impact on patient's condition. The reduced activity of the diaphragm and the weight of lung or abdominal organs in the supine position promote the formation of compression atelectasis.

Atelectasis formation

Compression atelectasis forms rapidly, whereas resorption atelectasis arises slowly and can be linked directly to small tidal volumes in combination with an FiO_2 of 1.0³. This second kind of atelectasis appears in regions with a low ventilation/perfusion ratio (V/Q). Perfusion enables transportation of oxygen from the alveolus into the blood much faster than oxygen enters the alveolus from the upper airways. Due to oxygen's rapid diffusing capacity and the pressure difference across the membrane, gas is 'sucked out' of the alveolus until it collapses. The pressure in the collapsed alveolus is almost zero, and re-opening of this reabsorption 'sticky' atelectasis requires a positive pressure of 30 – 35 cmH₂O. Compression atelectasis (in which gas remains in the occluded acinar compartment) can be re-opened more easily ('loose' atelectasis) with pressures between 10 and 12 cmH₂O. The onset of compression atelectasis depends on patient's position, for example during sleep or bed rest. In healthy patients, the areas of atelectasis and V/Q mismatch are reduced and minimized by physiological mechanisms (mainly changes in perfusion, Q). Co-morbidities that enhance the shunt fraction such as oedematous lungs [for example in acute respiratory distress syndrome (ARDS) or cardiac failure] have a markedly disturbed V/Q and lung function in these patients is worsened further as soon as anaesthesia is induced³.

Atelectasis during Anesthesia

Atelectasis is a major cause of impaired oxygenation during anaesthesia. The supine position alone reduces the functional residual capacity (FRC) by approximately 0.8 – 1.0 l. The FRC falls by another 0.4 – 0.5 l after induction of anaesthesia. Anesthetic induction results in a loss of inspiratory muscle tone and additionally, the loss of the dorsal flattening moves the diaphragm cephalad. The change in chest wall rigidity on one hand and the upwards shift of the diaphragm on the other decrease the transpulmonary pressure (the difference between alveolar and pleural pressure) and promote alveolar collapse and compression atelectasis. The formation of atelectasis occurs in up to 90% of patients, but it is observed particularly in obese patients in whom the regions of the lung that are atelectatic are increased by 10% compared to those of healthy patients, and can lead to clinical difficulty. Compression atelectasis can develop with spontaneous ventilation, resulting in a high shunt fraction independent of the mode of GA (intravenous or inhalational agent). The secondary reduced oxygenation due to formation of atelectasis under GA does not lead to intraoperative or postoperative morbidity in most patients, who will be extubated immediately at the end of surgery. Also mechanisms such as coughing or sneezing reopen their atelectasis. Nevertheless, some atelectasis is still present in healthy patients for 24 h after surgery, despite the area affected and, therefore, the clinical relevance may be small. However, these poorly aerated areas may become a site of infection⁶. In obese patients, 7.6% of the lung volume remains atelectatic after extubation, and this increases to 9.7% over the first 24 h after surgery. In these patients, the use of long-acting neuromuscular blocking agents should be avoided as they have been found to be a risk factor in developing hypoxemia and muscle weakness in the recovery room due to their inhibition of diaphragmatic muscle recovery after anaesthesia⁷. Our "healthy population"-pregnant women mimics obese patients.

Ventilation Induced Lung Injury

There is probably a strong link between ventilation induced lung injury (VILI) and the repetitive

shear stress applied to the lung parenchyma, the repetitive opening and closing of the atelectatic lung areas which finally destroys the lung tissue^{1,4}. Alveolar Recruitment Maneuver (RM) and positive end-expiratory pressure (PEEP) could ameliorate these atelectatic lung areas and improve lung mechanics and oxygenation^{3,4,8,9}. Repetitive recruitment and de-recruitment of collapsed lung units disrupt endothelial and epithelial cells, leading to increased permeability of the alveolo-capillary membrane and increased production of IL-1, IL-6, IL-8, and other inflammatory cytokines. Even short-term mechanical ventilation may act as a proinflammatory stimulus in non-injured lungs, and is dependent on the ventilator settings used¹.

Cesarean Section and General Anesthesia

Although cesarean section is usually performed under regional anesthesia, GA is always a possibility mainly in emergency situations. Pregnant women have healthy lungs but, on the other hand, pregnancy induces pathophysiological changes, which in combination with the induction of GA make these women prone to perioperative pulmonary complications. During pregnancy there is an increase in intraabdominal pressure, which causes cranial shift of the diaphragm and a reduction in FRC. The above changes become more pronounced in the supine position and predispose pregnant women to airway closure mainly in the dependent lung regions. Mechanical ventilation strategies, which could improve lung compliance and oxygenation in pregnant women, have never been investigated. In previous studies RM in combination with PEEP improved oxygenation and lung compliance after induction of anesthesia in healthy weight and obese patients¹⁰⁻¹⁶. The feasibility of the above ventilation strategy has been tested in laparoscopic and in major abdominal surgery too^{2,17,18}. The above concept resembles the lung-protective ventilation strategy (low tidal volumes, PEEP and RM), which is considered the best practice in critical care patients and which reduce mortality among patients with acute respiratory distress syndrome¹⁹. Total compliance (CT) is the relationship between changes in pressure (dp) and changes in volume (dv) of the lungs and thorax, as expressed by the equation: $CT \text{ (ml/cm H}_2\text{O)} = dv / dp$, where CT is a function of lung compliance (CL) and chest wall compliance (CCW): $CT = 1 / (1/CL + 1/CCW)$. In clinical practice, only CT is measured dynamically or statically, depending on whether a peak or plateau inspiratory dp is used for the CT calculation. During a positive pressure inspiration, transthoracic pressure increases to a peak value and then decreases to a lower plateau value. Transthoracic pressure decreases to a plateau value after the peak value because over time, gas is redistributed from stiff alveoli into more compliant alveoli. Less pressure is required to contain the same amount of gas, which explains why the pressure decreases. Dynamic compliance (Com_{dyn}) is the volume change divided by the peak inspiratory transthoracic pressure, and static compliance is the volume change divided by the plateau inspiratory transthoracic pressure. Therefore, static CT tends to be slightly greater than dynamic CT, although the measurements are quite similar in patients without pulmonary diseases.

Study objectives

Overall, we will test the hypothesis that the application of RM after delivery (during cesarean section) and then the maintenance of low tidal volume and PEEP throughout the operation, improves lung Com_{dyn} and perioperative oxygenation. The aim of the study is to prove that the above anesthetic technique is effective in preventing lung atelectasis, which is a major cause of abnormalities in lung mechanics, lung ventilation and gas exchange in women under cesarean section.

For safety reasons a **preliminary data analysis** has already been performed, before the beginning of the study. At all time points after intervention there is a significant difference in Com_{dyn} between the two groups ($p < 0.001$) while P_{peak} was significantly lower in the RM group too ($p = 0.021$). PO_2/FiO_2 and PO_2 were also significantly higher in the RM group vs the control group ($p < 0.001$). For more details see the preliminary data results section too.

Investigational Plan

Study Population and control group

This will be a prospective randomized double-blind clinical trial. After approval of the Institution Ethics Committee (General Hospital of Pyrgos Scientific and Ethic Committee), this trial will be conducted at Pyrgos General Hospital between April 2015 and September 2015. After having written informed consent for the participation to the study and in order to obtain GA, **ninety pregnant women** (the number originates from the power analysis - see below) with Anesthesiologists Physical status Classification scores (ASA) 1-2 will be scheduled for cesarean section. The **control group** will be managed with the usual anesthetic technique as mentioned before (no recruitment maneuver, no PEEP, usual tidal volumes). This is a no treatment concurrent control trial.

Inclusion criteria

Pregnant women > 18 years old with BMI < 40 will be eligible for the study. They should accept to have GA instead of regional anesthesia. Women with >130 beats/minute and concomitant pulmonary or/and cardiac pathologies will be excluded from the study (see next section too).

Exclusion criteria

The anesthetic technique will be the same for both groups of patients and is standardized as follows: Anesthesia will be induced with propofol (1.5-2 mg/kg), fentanyl (1 µg/kg) and rocuronium (1.5 mg/kg) and will be maintained with sevoflurane (minimal alveolar concentration 0.6-0.8) and fentanyl (400-450 µg). The minimum alveolar concentration of sevoflurane will be titrated from the attending anesthesiologist according to the arterial blood pressure (\pm 15-20 mmHg baseline) and beats per minute (\pm 10-15 baseline). Rocuronium for muscle paralysis will be used once, during induction of anesthesia to facilitate tracheal intubation (cuffed tube no 7-7.5-Portex, Inc., London) and without subsequent bolus doses, while at the end of the operation sugammadex (200 mg) will be used for neuromuscular block reversal. Intraoperatively ondasetron 4 mg, omeprazole 40 mg, paracetamol 1000 mg and Parecoxib 40 mg will be used to all the patients. The time between the end of preoxygenation and tracheal intubation must be standard (40-60 seconds) and will be recorded for all the patients. The Perioperative use of crystalloids and colloids, blood products and vasopressors will be recorded while fluid management will be left to the discretion of the attending anesthesiologist (Ringers Lactated). Hypotension (mean arterial pressure <60 mmHg) will be treated with ephedrine bolus 5 mg i.v and if insists bolus doses of hydroxyethylstarch (HES 130/0.4, Voluven; Fresenius Kabi, Germany) up to 1000 ml will be given. The standard monitors of the American Society of Anesthesiologists will be used while the radial artery will be cannulated for invasive blood pressure monitoring and blood gas measurements.

[figure not shown]
Ventilatory Management (time and method of RM)

Before induction of anesthesia preoxygenation (100% oxygen via face mask) for 2 minutes will be conducted to all the patients. After tracheal intubation, pregnant women in both groups will be mechanically ventilated (Datex-Ohmeda, Aestiva/5, Madison, WI, USA) with volume-controlled mode and with tidal volume at 8-ml/kg ideal body weights. Inspiratory to expiratory time ratio will be set to 1:2 while 40% oxygen fraction (balanced with air) will be used. The respiratory rate will be adjusted to maintain an end-tidal CO₂ between 30-35 mmHg and zero end-expiratory pressure will be applied (ZEEP). Immediately after delivery the control group of women will continue with exactly the same ventilator management while in the RM group lung recruitment will be achieved as follows:

[figure not shown]
The ventilator will be switched to pressure-controlled mode and the inspiratory time will be increased to 50% (inspiratory /expiratory ratio will be set to 1:1). The Peak inspiratory pressure (P_{peak}) will firstly be set to 20 cmH₂O (for 3 breaths) and then the investigators progressively will increase the positive end-expiratory pressure (PEEP) to have a P_{peak} up to 45-50 cmH₂O. The PEEP sequential will increase in four steps from 0 to 5 cmH₂O (for 3 breaths), from 5 to 10 cmH₂O (for 5 breaths), from 10 to 15 cmH₂O (for 7 breaths) and from 15 to 20 cmH₂O (for 10 breaths). The whole RM will last about 2 minutes. After the RM the investigators will use volume control ventilation again with the baseline settings mentioned above, tidal volume 6ml/kg and PEEP step-wise decrease to 8 cmH₂O, which must be maintained until the end of the operation. Lung recruitment in the RM group will not be repeated, as cesarean section is a short lasting operation. After completion of the operation and neuromuscular block reversal women in both groups will breath spontaneously before tracheal extubation and PEEP will be eliminated in the RM group. Also see flowchart below:

Study Design – Ventilatory Management Flowchart

RM Group

Control Group

Blinding procedure

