Because of the higher inspiratory pressures during RM and PEEP used, the $P_{plateau}$ and P_{peak} are anticipated to be significantly higher in the RM group, compared with those in the control group, and this would be a possible serious safety issue, as high alveolar pressures could result in pneumothorax or/and barotrauma. As the study involves young and healthy population, the investigators believe that the above safety issues will not be a serious problem of the study. A second safety issue will be the hemodynamic instability during RM. Patients with serious hemodynamic instability will be removed from the study, as already mentioned.

End of treatment

The treatment (RM) will start after delivery (3 minutes) and will last until the end of the surgery. Specifically, in the RM group the RM will be performed 3 minutes after delivery but PEEP and low tidal volume (which are part of the whole RM technique) will be continued until the end of the operation.

End of Study

The patients will be monitored throughout the operation and in the postoperative period too (see also the measurements section-primary end point, secondary measurements and follow up). The follow up will last for all the length of hospital stay. The length of hospital stay will be recorded while all the adverse events that will be occurred during this period they will be recorded too. For this kind of population the hospital stay is usually short (<5 days).

Adverse events:

Hemodynamic instability during the RM will be the most important adverse event of the study. During the RM all women should be closely monitored for the occurrence of hypotension or the administration of a fluid bolus or vasopressor medication to support haemodynamic variables. Of course during the whole course of anesthesia the need for vasopressor should be monitored. Possible differences between the two groups should be mentioned for all the above parameters (table 1).

Postoperative lung complications (pneumonia, atelectasis, pulmonary embolism, pneumothorax, acute lung injury (ALI), asthma, non-cardiogenic pulmonary oedema and severe hypercapnia) should also be recorded. As we will mainly include young and healthy population serious lung complications and differences between groups are not anticipated.

Preliminary Data Results

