For safety issues we decided to perform a preliminary data analysis before the beginning of the study. We used 7 patients in each group, and we will use these data analysis as an example of our data presentation plan and to show the most important measurements of our study. At all time points (3, 10 and 20 minutes) after intervention there is a significant difference in Com_{dyn} between the two groups ($p < 0.001$). The Com_{dyn} is much higher in the RM group vs control group (table 2). The significant difference in lung Com_{dyn} depicts in figure 1a too.

Post intervention the peak inspiratory pressure at all time points (3, 10 and 20 minutes) is significantly lower in the RM group compared to control group ($p = 0.021$, table 2, figure 1b).

PO_2/F_iO_2 and PO_2 are also significantly higher in the RM group vs the control group ($p < 0.001$) at all time points post intervention (3, 10 and 20 minutes) while PO_2 is also significantly higher in the RM vs control group postoperatively ($p < 0.001$). SpO_2 is significantly difference between the two groups at 10 and 20 minutes post intervention and postoperatively ($p = 0.04$) – table 2

There are no significant differences in expiratory tidal volume, minute volume, end tidal CO_2 , PCO_2 and in hemodynamic data between the two groups (tables 2, 3).

[figure not shown]
Table 2. Respiratory Mechanics and Gas Exchange in the two groups of pregnant women (recruitment vs control, respectively-**Example**). Data are presented as mean \pm SD. The P-value corresponds to the tests of between subject main effects using the mixed Anova test (recruitment vs control group). The two groups were also compared separately at each time point using the independent two-sample t-test (*) and (**). (*) denotes significant differences from the control when $P < 0.01$ while (**) is used whenever $P < 0.05$. PaO₂, arterial blood oxygen; PaCO₂, arterial blood CO₂; SpO₂, arterial blood oxygen saturation; FiO₂, oxygen concentration.

	Baseline	After intervention (minutes)			Postoperative	P-value
		3 min	10 min	20 min		
Peak Inspiratory Pressure (cmH₂O)					-	0.021
Recruitment	23.9 (2.9)	19.9 (2.5)*	20.2 (2.9)*	20.3 (3.0)*		
Control	23.0 (2.8)	22.1 (2.8)	22.5 (2.7)	22.2 (2.7)		
Com_{dyn} (ml/cmH₂O)					-	<0.001
Recruitment	33.6 (6.8)	51.4 (12.8)*	49.9 (11.2)*	49.7 (10.9)*		
Control	31.1 (7.9)	29.6 (7.2)	30.6 (8.1)	30.9 (8.1)		
PaO₂ (mmHg)						<0.001
Recruitment	211.7 (10.6)	242.7 (26.9)*	242.1 (22.0)*	243.5 (27.6)*	108.4 (6.7)*	

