Appendix 5 - Haemodynamic patient's data

Patient ID:	Baseline	3 minutes	10 minutes	20 minutes	Postoperative
SBP (mmHg)	X	X	X	X	X
DBP (mmHg)	X	X	X	X	X
MAP (mmHg)	X	X	X	X	X
BPM	X	X	X	X	X

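### Table 3 compares blood pressure and heart rate that sevoflurane is titrated to hold near baseline, and no form or table records sevoflurane, so any haemodynamic effect of the recruitment strategy may be understated by an unknown amount

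*Protocol*

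**What the plan says.** **Titration.** Protocol, Anesthetic technique, applies one technique to both arms. Maintenance is with "sevoflurane (minimal alveolar concentration 0.6-0.8" MAC. Within it, "The minimum alveolar concentration of sevoflurane will be titrated from the attending anesthesiologist according to the arterial blood pressure" and heart rate, with bands of 15-20 mmHg and 10-15 beats per minute around baseline.

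**Rescue and recording.** The same section states "Hypotension (mean arterial pressure <60 mmHg) will be treated with ephedrine bolus 5 mg i.v", with colloid if hypotension persists. It adds: "The Perioperative use of crystalloids and colloids, blood products and vasopressors will be recorded". Sevoflurane is not in that list.

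**Comparison.** Protocol, Statistical analysis, compares haemodynamic variables between arms by mixed ANOVA, with a two-sample t-test at each time point. Table 3 shows systolic, diastolic and mean pressure and heart rate by arm at baseline, 3, 10 and 20 minutes. On the example data, Preliminary Data Results reports no significant differences in several ventilation variables "and in hemodynamic data between the two groups (tables 2, 3").

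**Importance.** Protocol, Adverse events: "Hemodynamic instability during the RM will be the most important adverse event of the study". That section also asks for hypotension, fluid boluses and vasopressor use to be monitored, with differences between arms reported through Table 1.

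**Forms.** Patients Records lists four files, Appendices 3 to 6. "Appendix 5 - Haemodynamic patient's data" holds three pressures and heart rate. Appendix 3 and Table 1 hold crystalloids, colloids, blood and ephedrine. None has a field for sevoflurane dose, MAC or end-tidal concentration.

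**The concern.** Pressure and heart rate are both the outcomes in Table 3 and the variables that the anaesthetist steers. If the RM and PEEP lower pressure and the anaesthetist responds with less sevoflurane, part of the effect moves out of the pressure reading and into the anaesthetic dose. Similar pressures reached at equal depth, and similar pressures reached with lighter anaesthesia in the RM arm, would look the same in Table 3.

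An analysis plan cannot repair this later, because it cannot recover readings that were never taken. Blinding adds to the concern. The Blinding procedure section says that the primary investigator knows the allocation and that the second anaesthesiologist enters after the RM; the Randomization section names these two as the anaesthetists for all cases. By inference, whoever adjusts sevoflurane during the RM knows the arm, and an arm-specific adjustment would leave no record.

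**Working it through.** The plan gives no figure on this point, so there is none to reproduce. The checks below ask what is captured, what the example data show, and how much titration could matter under stated assumptions.

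**1. Where the record has a gap.** Mean arterial pressure (MAP) at baseline in Table 3 is 88.8 mmHg (RM) and 88.4 mmHg (control). Ephedrine starts below 60 mmHg, so an average woman must fall by 88.8 − 60 = 28.8 or 88.4 − 60 = 28.4 mmHg before the recorded treatment is triggered. The titration band is 15-20 mmHg. Between about 15-20 and 28 mmHg, the only response the protocol specifies is the unrecorded one. Fluids are at the anaesthetist's discretion and are recorded as one total per woman, not by time point.

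**2. What the example data show.** Mean changes from baseline in Table 3 run from −1.6 mmHg (control diastolic, 72.7 to 71.1) to −6.5 mmHg (control systolic, 125.7 to 119.2), and from −2.6 to −5.2 beats per minute. All lie well inside the bands. MAP at 3 minutes differs by 83.4 − 85.8 = −2.4 mmHg (RM minus control). The Welch 95% CI is −6.3 to 1.5 with the n = 40 and 41 in the table's title, or −12.8 to 8.0 with the 7 per group stated in Preliminary Data Results (the two counts need reconciling). At 10 and 20 minutes the differences are +0.6 and +1.4 mmHg. The pattern fits a neutral RM, and it also fits a modest effect offset by lighter anaesthesia.

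**3. Illustrative model.** Assumptions, none from the documents except the floors and the group size:
- the band applies to MAP (the protocol says only arterial blood pressure);
- without titration, the MAP change is normal with SD 10, mean −4 mmHg in controls and −4 − D in the RM arm;
- titration holds every woman at a floor c of −15 or −20 mmHg;
- 45 women per arm, two-sided t-test at 0.05.

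With a = (c − μ)/σ, the floored mean is cΦ(a) + μ(1 − Φ(a)) + σφ(a), and the share of women at the floor is Φ(a). Example, D = 10 and c = −15: the control mean is −3.3 and the RM mean −10.5, a difference of 7.2.

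| True D | Floor | Difference seen | Loss | Power | Power, no titration |
|---|---|---|---|---|---|
| 5 | −15 | 4.0 | 20% | 0.62 | 0.65 |
| 5 | −20 | 4.5 | 9% | 0.64 | 0.65 |
| 10 | −15 | 7.2 | 28% | 0.993 | 0.997 |
| 10 | −20 | 8.5 | 15% | 0.996 | 0.997 |
| 20 | −15 | 10.7 | 47% | 1.00 | 1.00 |
| 20 | −20 | 13.9 | 30% | 1.00 | 1.00 |

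Power barely moves because the floor shrinks the spread as well as the difference: at D = 10 and c = −15 the SDs fall from 10 to 8.9 (control) and 6.2 (RM).

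At D = 10 the share of women at the floor is 46% (RM) against 14% (control) for c = −15, and 27% against 5% for c = −20. In this model the contrast in need for titration is large, and it is the part that the forms do not hold.

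**4. Sensitivity to the mechanism.** Suppose instead that a fixed share of a true 8 mmHg fall is titrated away while the SD stays at √((10.1² + 7.4²)/2) = 8.85 mmHg, from the 3-minute MAP SDs. Power with 45 per arm is then 0.99, 0.90, 0.57 and 0.19 for shares of 0, 25, 50 and 75%. No document gives that share, so this shows only that the answer depends on something the trial will not have measured.

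**The case against.** A reader might infer that a null Table 3 is close to guaranteed, or that the protocol wrongly declares the RM haemodynamically neutral. The documents support neither.

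- **Power.** Under the floor model, a true 10 mmHg difference is still detected with power of 0.99 or more. The lower powers in step 4 rest on an assumed share.
- **Wording.** The Abstract states an expectation of no difference, and Preliminary Data Results reports non-significance in example data. Neither claims neutrality.
- **Other outputs.** Table 3 is not the only haemodynamic evidence. Hypotension, fluid boluses and vasopressors are to be compared through Table 1, persistent MAP below 50 mmHg leads to removal, and reasons for non-completion are to be reported. Larger falls are therefore visible.
- **Bounded masking.** The 0.6-0.8 MAC range limits how far sevoflurane can offset a fall, so a perfect floor is an idealisation and the true attenuation may be smaller.
- **Recording.** The appendices are not exhaustive: the interval from preoxygenation to intubation and estimated blood loss are named elsewhere but have no field there. What can be said is that no form, table or sentence provides for recording sevoflurane.
- **Validity.** The same rule applies in both arms, so the randomised contrast is a fair estimate of haemodynamics under managed anaesthesia. Haemodynamics are neither the primary nor a listed secondary endpoint.

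All of this stands. It lowers the weight of the point without removing it: falls too small to trigger ephedrine can still be absorbed by an unrecorded adjustment, and the comparison bears on the harm that the protocol ranks first.

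**Conclusion.** The point holds as one of attenuation and limited interpretability. Table 3 estimates haemodynamics under titrated anaesthesia. Any effect of the RM and PEEP on pressure or heart rate may be understated, and the part absorbed by lighter anaesthesia will not be visible.

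The amount cannot be calculated from the documents. In the floor model a true 10-20 mmHg difference is understated by 15-47%, with almost no loss of power. Those figures rest on an assumed SD of 10 mmHg, an assumed control change of −4 mmHg and perfect titration at the band. A false null is not demonstrated. This is a low-cost improvement to data capture and wording, and does not correct an error in the design.

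**What to change.** 1. Add sevoflurane MAC or end-tidal concentration at baseline, 3, 10 and 20 minutes to Appendix 5.
2. Tabulate it by arm in Table 3 beside pressure and heart rate.
3. Interpret Table 3 together with the ephedrine, fluid and blood data in Table 1 and the reasons for removal.
4. Describe the haemodynamic result as obtained under titrated anaesthesia.

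The titration rule and the treatment of hypotension are unchanged. The cost is four extra readings per woman (4 × 90 = 360 in all), one extra row in Table 3 and one reworded sentence.
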